COMIRB Protocol

COLORADO MULTIPLE INSTITUTIONAL REVIEW BOARD
[name] [contact] [contact]

Protocol #: 17-0827

Project Title: Validation Study of the WatchPAT 200 in the Diagnosis of Obstructive Sleep Apnea in Children 4-12 Years of Age

Principal Investigator: [name]

Version Date: 01Jun2017

I. Hypotheses:

We hypothesize that the WatchPAT™ 200U (Peripheral arterial tonometry recorder; Itamar Medical, Caesarea, Israel), which is a wrist worn, non-invasive, ambulatory sleep recorder device based on peripheral arterial tone (PAT) signal, pulse rate, actigraphy and pulse oximetry will be able to detect obstructive sleep apnea in children 4 to 12 years of age as effectively as an overnight, attended, in-laboratory polysomnogram.

Our Specific Aims:

1. To evaluate the accuracy of the WatchPAT 200 device compared to an in-laboratory polysomnogram (PSG) in detecting obstructive sleep apnea (OSA) through measurement of the peripheral arterial tone apnea hypopnea index (PAHI) in children 4-12 years of age who are referred to the Children's Hospital Colorado (CHCO) sleep lab for a diagnostic PSG due to concerns for possible OSA.
2. To evaluate the diagnostic agreement of the WatchPAT 200 device in detecting between normal sleep and mild (≥ 2 events per hour) versus moderate to severe obstructive sleep apnea (OAHI of ≥ 5 events per hour) in children 4-12 years of age compared to an in-laboratory PSG.
3. To evaluate the accuracy of the WatchPAT 200 device in measuring other parameters such as the PAT Respiratory disturbance index (PRDI), oxygen desaturation index (ODI), heart rate and body position compared to an in-laboratory PSG.
4. To evaluate the accuracy of the WatchPAT 200 device in determining sleep architecture compared to an in-laboratory polysomnogram.

II. Background and Significance:

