It requires minimal cleaning, preparation and handling before or after patient use. Fully automated reports are also generated within minutes; thereby helping increase workflow efficiency and hopefully diagnose and treat patients in a more timely manner. Furthermore, it has the advantage of eliminating interscorer variability. This technology has the potential to be an accurate and safe alternative in diagnosing OSA in the younger age group, where the disease is known to be prevalent.

III. Preliminary Studies/Progress Report:

There have been validation studies which were mostly performed in adult patients. Weimin et al. studied 28 adults with suspected OSA who underwent an inpatient polysomnogram while wearing a WatchPAT 200. The study showed comparable accuracy in detecting OSA based on AHI (mean PSG score for events/hour was 23 ± 21.55 compared to a mean score of 25.00 ± 19.09 for the WatchPAT, $r=0.92$, $P<0.001$). It also provided a reasonably accurate estimation of sleep and wakefulness (agreement was $89\pm6\%$).³⁷ In another validation research using the WatchPAT200, Gan et al studied 20 patients with suspected OSA who also had simultaneous PSG and WatchPAT200 concurrently at the sleep lab. The study showed the WatchPAT being 100% sensitive when compared to PSG for detecting mild OSA and concluded that it is a good screening test for the undiagnosed general population. They study showed 100% specificity when compared to PSG for severe OSA suggesting that it is a good diagnostic test for people with a high suspicion of OSA.³⁸

A meta-analysis by Yalamanchali et al. on 14 studies assessing the correlation of sleep indexes between PAT devices and PSG in adults (aged >18 years). The researchers found high overall correlation of the RDI and AHI ($r=0.889$ [95% CI, 0.862-0.911]; $P<.001$). Studies comparing the RDI between PAT and PSG had a combined correlation of 0.879 (95% CI, 0.849-0.904; $P < .001$); those comparing the AHI, 0.893 (0.857-0.920; $P < .001$); and those comparing the ODI, 0.942 (0.894-0.969; $P < .001$).³⁶

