Hedner et al. specifically studied the agreement in determining sleep architecture between the WatchPAT 100 and an in laboratory polysomnogram. The overall agreement in detecting light/deep and REM sleep were $88.6\% \pm 5.9\%$ and $88.7\% \pm 5.5\%$ respectively. OSA severity did not affect the sensitivity and specificity of the algorithm. The Cohen K coefficient for detecting all sleep stages: sleep from wake, REM from NREM sleep and deep from light sleep were 0.48, 0.55, 0.59 and 0.46, respectively. They concluded that analysis of signals from the PAT recorder can detect sleep stages with moderate agreement to more standard techniques in normal subjects and OSA patients.³⁹

There are a few studies looking into the utility of the WatchPAT in the younger population. A pilot study by Serra et al was performed to evaluate the efficiency of the WatchPAT in determining pediatric sleep disordered breathing (PSDB) in 28 children (5-12 years) presenting with symptoms of SDB but with a negative nocturnal pulse oximetry test. The study showed that in these children, the WatchPAT was able to detect sleep disordered breathing in 10/28 (35.7%) using a cut off of PAT Respiratory Disturbance Index (PRDI) of 5 in patients who tested negative during a nocturnal oximetry test. When the threshold for SDB was changed to a PAHI of >1, the number of positive patients for PSDB increased to 17/28 (60.7%).⁴⁰ A study by Su et al. examined 50 children aged 3-11 years with symptoms of snoring and assessed the sensitivity and specificity in the diagnosis of OSA using a PAT portable sleep monitor and compared it to an in-lab polysomnogram as the reference standard. The study found that in the 6-11 year old age group, 14 cases were diagnosed with OSA by the PAT and polysomnogram; however, in the 3-5 year age group, only six children were diagnosed with OSA and there was a significant difference between the PAT and PSG ($p<0.05$).⁴¹ More validation studies in this age group is needed.

IV. Research Methods

A. Outcome Measure(s):

Primary outcome: Peripheral arterial tone apnea-hypopnea index (PAHI) and severity index
Secondary outcomes: Peripheral arterial tone respiratory disturbance index (PRDI),

Oxygen desaturation index (ODI), Sleep staging and sleep time, Oxygen saturation, Heart rate, Body Position

B. Description of Population to be Enrolled:

Inclusion Criteria:

1. Age 4 through 12 years of age.

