Summary statistics of basic demographics on the study population will be calculated. Wilcoxon signed rank test will compare median outcomes of interest (Total AHI, OAHI,etc) between WatchPAT 200 and PSG Lab testing. Spearman's correlation coefficient will be used to measure correlation between WatchPAT 200 and Lab testing. Bland Altman plots will graphically assess modality correlation. Sensitivity and specificity with 95% confidence intervals of WatchPAT 200 will be calculated for three cutoffs of the outcomes (<2, <5, and <10 events/hour) using the PSG lab study as the gold standard. Finally, test agreement on apnea categories will be assessed using Cohen's Kappa statistics fixing OSA diagnosis as dichotomized as none or mild (OAHI <2 events/hour) versus moderate or severe (OAHI \geq 5 events/hour) disease. Other analyses may be conducted on specific strata of participants, based on either patient age or BMI percentile.

Power and Sample Size

Power and sample size were calculated for the primary aim of the study using Power Analysis & Sample Size Software, PASS 15.0 (NCSS, LLC. Kaysville, Utah, USA). The primary aim is to assess whether the PatWatch device agrees with PSG laboratory studies in its ability to detect OSA. For the power analysis OSA diagnosis was dichotomized as non or mild (AHI<4.5) versus moderate or severe (AHI \geq 4.5) disease.

From previous clinical sleep study experience, (from personal review of PSG's performed at the Main Campus of Children's Hospital Colorado in the month of February 2017), investigators anticipate roughly 11 PSG sleep studies per month with about 2 patients diagnosed with OSA.

In a test for agreement between two raters using the Kappa statistic, a sample size of 120 participants achieves 80% power to detect a true Kappa value of 0.95 in a test of H0: Kappa \leq κ_0 vs. H1: Kappa $>$ κ_0 when there are 2 categories with frequencies equal to 0.82 and 0.18. This power calculation is based on a significance level of alpha = 0.05.

Investigators also wished to determine whether the difference of proportions of individuals detected to have OSA between testing modalities was no larger than 5%.

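### For the continuous PAHI the plan commits to no bias, limits of agreement or confidence intervals: Bland-Altman is planned as a plot of correlation, and Wilcoxon and Spearman cannot say how far one reading may lie from PSG

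*Combined protocol and SAP*

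**What the plan says.** Section IV.A lists "Primary outcome: Peripheral arterial tone apnea-hypopnea index (PAHI) and severity index". Aim 1 in section I judges the device's accuracy through that index. Aim 3 extends the question to accuracy "in measuring other parameters such as the PAT Respiratory disturbance index (PRDI), oxygen desaturation index (ODI), heart rate and body position".

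Section IV.F (Statistical Analysis plan) gives three analyses for continuous measures:

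- "Wilcoxon signed rank test will compare median outcomes of interest", with total AHI and OAHI as examples;
- Spearman's "correlation coefficient will be used to measure correlation between WatchPAT 200 and Lab testing";
- "Bland Altman plots will graphically assess modality correlation".

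The plan mentions no bias, no limits of agreement, no confidence interval for either, and no method for an index whose differences may widen as it rises. The only confidence intervals it promises are for sensitivity and specificity at cutoffs of 2, 5 and 10 events/hour. Cohen's kappa and the 5% non-inferiority margin (Power and Sample Size) concern categories and proportions.

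**The concern.** A validation study of a device that reports an index should tell the user how far a reading may lie from the reference. The plan's own cutoffs are 2, 5 and 10 events/hour, so for a child who reads near one of them the size of the error decides whether the reading can be trusted.

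None of the three planned analyses is committed to giving that size. Spearman measures ranking, so a device that reads exactly double in every child scores 1.00. Wilcoxon looks for a systematic shift, so a device that scatters widely but evenly around PSG passes unnoticed. Bland-Altman is the right tool, but its stated purpose is correlation and it is described only as a graph.

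The gap is wider for some Aim 3 measures. Heart rate has no cutoff in events/hour, so sensitivity and specificity as planned do not apply to it, and no other numerical analysis of agreement is listed.

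**Working it through.** The plan states no figure here to reproduce. The check has two parts: an example from the protocol's background, and a simulation on stated assumptions.

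**1. A high correlation can sit beside wide limits.** Section III cites a study of 28 adults: "mean PSG score for events/hour was 23 ± 21.55 compared to a mean score of 25.00 ± 19.09 for the WatchPAT", with r = 0.92. Take ± as the SD and r as Pearson.

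- SD of differences = √(SD₁² + SD₂² − 2·r·SD₁·SD₂) = √(21.55² + 19.09² − 2 × 0.92 × 21.55 × 19.09) = 8.48
- Bias = 25.00 − 23 = 2.0
- Limits = 2.0 ± 1.96 × 8.48 = −14.6 to +18.6 events/h
- Rounding of r: 0.915 gives −15.1 to 19.1, and 0.925 gives −14.1 to 18.1

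These are adults with a mean index of 23/h, so the figures illustrate the principle and do not predict the paediatric result.

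**2. Simulation set-up.** The plan gives no distribution for the index, so the following are assumptions.

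- Log-normal index with 18% at or above 4.5/h (the prevalence and cut in Power and Sample Size). Log SD is 0.8, 1.0 or 1.2, which gives medians of 2.16, 1.80 and 1.50/h.
- n = 147, the plan's non-inferiority sample size.
- An unbiased device with log-scale correlation 0.893. The value is borrowed from the adult meta-analysis in section III ("those comparing the AHI, 0.893"); using it on the log scale in children is an assumption.
- Run with and without Poisson counting noise over an assumed 7 h of sleep.

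**3. What the planned tests show for that device.** Wilcoxon rejects in about 4-6% of trials, so it sees nothing. Median Spearman is 0.88, or 0.79-0.81 with counting noise. Conversely, for a device that doubles the index (log error SD 0.15), Spearman is 0.98-0.99 and Wilcoxon rejects in 100%. Each test catches one kind of fault, and neither gives its size for an individual child.

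**4. What limits of agreement show for that device.** For limits that vary with the mean, regress the difference on the mean, then the absolute residual on the mean. The half-width is 1.96 × √(π/2) × the fitted absolute residual.

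| Log SD | 5/h, no counts | 2/h, counts | 5/h, counts | 10/h, counts |
|---|---|---|---|---|
| 0.8 | ±3.7 | ±2.0 | ±4.3 | ±8.1 |
| 1.0 | ±4.6 | ±2.3 | ±5.1 | ±9.8 |
| 1.2 | ±5.5 | ±2.5 | ±6.0 | ±11.9 |

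**5. Why the default version is not enough.** Constant-width limits (bias ± 1.96 SD) cover about 100% of differences below 2/h but only about 43-54% at 10/h or more: too wide for most children and too narrow for the most affected. Regression-based limits fitted at n = 147 (with counts) cover 91% below 1/h, 95-97% at 1-5/h, 90-93% at 5-10/h and 85-91% at 10/h or more.

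**The case against.** The strongest reply is that this is a reporting detail. Bland-Altman is the right method, such plots usually carry lines for the mean difference and limits, and a Wilcoxon comparison is usually reported with medians. Some of the missing numbers would therefore probably appear. That stands, and it rules out reading the plan as having no agreement method at all. It does not supply confidence intervals, correct the stated purpose, or deal with the uneven coverage of standard lines on a skewed index.

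A second reply is that the study is a pilot and its powered aim is agreement in detecting OSA. That also stands: kappa, sensitivity and specificity with confidence intervals, and the 5% margin address detection, and nothing here questions them. For the simulated device, sensitivity at 5/h would be 0.67-0.72, so misclassification would be visible. Sensitivity does not say how far a reading lies from PSG, however, and PAHI is itself a named primary outcome.

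Three stronger readings might be inferred, and the documents support none of them.

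- *A poor device would pass the planned continuous tests.* The plan sets no pass rule for Wilcoxon or Spearman and never says that a non-significant Wilcoxon shows agreement.
- *Wilcoxon would nearly always condemn a close device with a small offset.* For a 5% offset, about 95% rejection needs an assumed log error SD of 0.15 and no counting noise. It falls to 36-45% with 7 h counts and to 55-66% with log error SD 0.30.
- *The adult limits of −14.6 to +18.6/h apply to these children.* They come from a population with much higher indices.

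**Conclusion.** The point holds for the continuous index only. Section IV.F commits to no bias, limits of agreement or confidence intervals for PAHI, and gives Bland-Altman the wrong purpose. Detection, the powered aim, is unaffected.

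That reading rests on the text alone. The size rests on the assumed log-normal index, the 18% prevalence at 4.5/h, log SD 0.8-1.2 and the borrowed adult correlation. On those assumptions a device without offset and with Spearman near 0.8-0.9 could still differ from PSG by about ±3.7 to ±6/h at 5/h, and constant-width limits would cover only about half of the differences at 10/h or more. The true paediatric spread is unknown, which is a reason to commit to estimating it. This should be changed, but it does not threaten the study's main inference.

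**What to change.** In section IV.F:

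- Replace *correlation* with *agreement* as the purpose of the Bland-Altman analysis.
- Report bias and 95% limits of agreement, with 95% confidence intervals, for PAHI against one named PSG index. The plan now lists total AHI and OAHI as examples without choosing.
- If the spread of differences grows with the mean, use limits that vary with the mean (regression-based or log-scale) and report them at 2 and 5/h. Treat any limit at 10/h as descriptive.
- Use Wilcoxon only as a check for offset and Spearman only as a description.
- Report continuous Aim 3 measures such as ODI and heart rate in the same way.

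The cost is SAP wording and minor programming, with no extra participants. Limits that vary with the mean are less familiar to readers. At n = 147, under the same assumptions, the confidence interval half-width for the regression-based limits is about ±0.4-0.7/h at 2/h and ±1.1-1.8/h at 5/h. At 10/h it is ±2.9-4.6/h, because only about 4 to 8 children lie there. Bootstrap intervals for these limits fall short of the nominal 95%: about 87-91% coverage at 5/h and 83-90% at 10/h. That should be stated with the results. The usual normal-theory interval for a constant-width limit (±0.28 SD) does worse, covering 32-66%.

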Data to be collected from all subjects include results of baseline/diagnostic polysomnogram (PSG) and sleep parameter indices (apnea-hypopnea index, etc.). Upon completion of the sleep study, the clinically indicated study will be scored by a physician as normal. The PSG will then be scored again by a single-point dedicated sleep technician research scorer to ensure consistent scoring methods between subjects and clinical sleep study scorers. The data collected by the WatchPAT 200 device will be scored through the WatchPAT 200 software installed on a local encrypted and password-protected computer. Additional information that may be collected includes medical history, medications, and basic demographic information.

D. Description, Risks and Justification of Procedures and Data Collection Tools:

The use of the WatchPAT 200 device has very low risk to the subject. This is a closed system that is worn on the wrist and finger that is not invasive to the patient. The device includes connections the EKG leads and other standard markers that are included in a clinical polysomnogram but are

optional and can be removed from the device between subjects. There is a slight risk of irritation of wearing the device as patients will most likely not be used to wearing someone on their wrists during their habitual sleep episodes.

E. Potential Scientific Problems:

There are no potential scientific problems at this time.

F. Data Analysis Plan:

Statistical Analysis plan

Data collected for a participant will be excluded from the analysis if any of the following: 1) WatchPAT 200 sleep time of less than 4 hours, 2) Lab test sleep time of less than 4 hours, 3) poor quality Lab test, consisting of a substantial portion of the Lab test not assessable, as determined by research staff occurred and 4) all WatchPAT 200 channel information not available from the study. The primary goal of the study is to validate and compare two sleep study modalities: 1) WatchPAT 200 and 2) Lab Testing sleep apnea.

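### The kappa categories leave OAHI 2 to <5 unclassified, conflict with Aim 2, and are not the split on which the kappa test was sized

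*Combined protocol and SAP*

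**What the plan says.** Section IV.F, Statistical Analysis plan, sets up Cohen's kappa with the OSA diagnosis "dichotomized as none or mild (OAHI <2 events/hour) versus moderate or severe", with the upper category at OAHI 5 or more.

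The same split is described differently in two other places:

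- Section I, Aim 2, contrasts "normal sleep and mild (≥ 2 events per hour) versus moderate to severe obstructive sleep apnea (OAHI of ≥ 5 events per hour". Mild starts at 2 and sits with normal sleep.
- Section IV.F, Power and Sample Size, states: "For the power analysis OSA diagnosis was dichotomized as non or mild (AHI<4.5) versus moderate or severe" (AHI 4.5 or more). The kappa calculation there applies "when there are 2 categories with frequencies equal to 0.82 and 0.18".

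Two further passages bear on the point. The exclusion paragraph ("Data collected for a participant will be excluded from the analysis if any of the following") gives four reasons: short sleep time on either test, a poor-quality laboratory study, and missing device channels. None is an index value. The sensitivity and specificity analysis uses "three cutoffs of the outcomes (<2, <5, and <10 events/hour"), so 2 and 5 are separate cutoffs there and 4.5 is not among them.

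**The concern.** A two-category kappa needs every analysed child to fall in one of two categories on both tests. As printed, a value from 2 to <5 falls in neither, and the plan gives no rule for it. Whoever runs the analysis must choose one, possibly after seeing the data.

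This matters because kappa is the first statistic sized for the primary aim. The children in the gap lie next to the cut, where two imperfectly correlated measurements are most likely to disagree. Leaving them out removes much of the disagreement that the study is meant to measure.

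**Working it through.** **1. The three definitions side by side**

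| Place | Lower group | Upper group | Index | Covers every value? |
|---|---|---|---|---|
| Aim 2 | normal plus mild, mild from 2 | ≥5 | OAHI | yes, if mild runs up to 5 |
| Kappa analysis | <2 | ≥5 | OAHI | no: 2 to <5 is missing |
| Kappa sizing | <4.5 | ≥4.5 | AHI | yes: 0.82 + 0.18 = 1 |

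The lower group in the kappa analysis is labelled as including mild disease, yet it contains no child who is mild under Aim 2. AHI and OAHI are listed as separate outcomes in section IV.F, so the sizing differs in index as well as cut.

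**2. The plan's own figure, N = 120**

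The null value κ0 is printed only as a symbol, so 120 cannot be reproduced from the stated inputs alone. The large-sample formula is n = [(z_α·τ(κ0) + z_β·τ(κ1)) / (κ1 − κ0)]², with τ² = (1−κ){(1−κ)(1−2κ) + κ(2−κ)/[2p(1−p)]}. With p = 0.18 and κ1 = 0.95:

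- Solving one-sided for n = 120 gives κ0 = 0.7997.
- With κ0 = 0.80, τ(0.80) = 0.7915 and τ(0.95) = 0.4083, so n = [(1.645 × 0.7915 + 0.8416 × 0.4083)/0.15]² = 120.3.

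So 120 fits a one-sided 0.05 test against κ0 of about 0.80, with every child classified.

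**3. Headcount and power**

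150 − 120 = 30, and 30/150 = 20%. The kappa table falls below 120 only if more than 20% of enrolled children are in the band on either test. That is not the same as losing power, because dropping the band raises the upper-group share. Suppose a fraction g is dropped and 18% of all children stay in the upper group. Then n = 150(1−g) and p = 0.18/(1−g). For g from 10% to 40%, n runs from 135 to 90 and power from 90% to 84% (κ0 = 0.80 assumed).

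**4. Effect on kappa: one worked case**

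The documents give no index distribution, so every input here is assumed: log-normal indices, the same distribution on both tests, 18% at or above 5, median 1.0/h, and log-scale correlation 0.893. The correlation is borrowed from the adult meta-analysis in section III ("those comparing the AHI, 0.893"), which does not state a scale. The log SD is ln(5/1.0)/0.915 = 1.76. Bivariate-normal cell probabilities:

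| PSG \ device | <2 | 2 to <5 | ≥5 |
|---|---|---|---|
| <2 | 0.5846 | 0.0589 | 0.0098 |
| 2 to <5 | 0.0589 | 0.0692 | 0.0387 |
| ≥5 | 0.0098 | 0.0387 | 0.1315 |

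- *Band in the lower group.* Observed agreement is (0.5846 + 2 × 0.0589 + 0.0692) + 0.1315 = 0.903. Chance agreement is 0.82² + 0.18² = 0.705. Kappa = (0.903 − 0.705)/0.295 = 0.67.
- *Pairs dropped if either value is in the band.* Kept: 0.5846 + 2 × 0.0098 + 0.1315 = 0.7357, or 110 of 150. Observed agreement is 0.7161/0.7357 = 0.973. The upper share is 0.1413/0.7357 = 0.192, so chance agreement is 0.690. Kappa = (0.973 − 0.690)/0.310 = 0.91.

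**5. Range over the assumptions**

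Correlation 0.893, no device bias, medians 0.3 to 2.5/h:

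| Handling of 2 to <5 | Kappa | Children left of 150 |
|---|---|---|
| Lower group (single cut 5) | 0.67 | 150 |
| Upper group (single cut 2) | 0.69–0.70 | 150 |
| Dropped if on PSG | about 0.74–0.79 | 85–137 |
| Dropped if on either test, medians 0.3–0.5 | 0.83–0.86 | 122–127 |
| Dropped if on either test, medians 1.0–2.5 | 0.91–1.00 | 67–110 |

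- At correlation 0.80, a single cut at 5 gives 0.55 and either-test dropping gives 0.69–0.97.
- At correlation 0.95, the figures are 0.78 and 0.93–1.00.
- If the device reads 0.67 to 2.0 times PSG (correlation 0.893, medians 0.5–2.5/h), either-test dropping still raises kappa by at least 0.17.
- Dropping on PSG alone can go either way. At 1.5 times, with the device split at 2, it gives 0.39–0.68, against 0.53–0.66 for a single cut at 5.

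**The case against.** The strongest reply is that the documents nearly resolve the gap themselves. The kappa sentence speaks of a dichotomy and places mild disease in the lower group. Aim 2 makes 2 to <5 mild, and the sizing uses one exhaustive cut. The natural reading is a slip in one bound. On that reading nothing is dropped and nothing is inflated, and only OAHI 5 against AHI 4.5 remains. The high kappas belong to a deletion rule that the plan never states.

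That reading is plausible, but it is not certain. The plan also uses 2 as a cutoff in its own right, and no passage says which bound is wrong. A different analyst could follow the printed categories literally.

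Other objections stand:

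- Falling below 120 should not be read as underpowering (step 3).
- The 0.18 matches 2 of about 11 patients (2/11 = 0.182) diagnosed with OSA, with no index or cutoff given. It is not clearly tied to 4.5, so renaming the cut would not by itself change 120.
- The magnitudes come from a model, not from trial data. The lowest median, 0.3/h, needs a log SD of 3.07 and is hard to believe, though removing it does not change the direction.
- Sensitivity and specificity at 5, the Wilcoxon, Spearman and Bland–Altman analyses and the 147-participant non-inferiority test are unaffected by the gap.

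**Conclusion.** The concern holds. On the printed text alone, OAHI 2 to <5 has no category, the kappa split contradicts Aim 2, and the kappa test was sized on a different index and cut. None of this depends on the model.

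The size of the effect does. Under the assumptions in step 4, kappa is 0.67 with the band in the lower group and 0.83 to 1.00 if either-test pairs are dropped. Across the no-bias scenarios with correlations 0.80 to 0.95, a single cut at 5 stays below the implied null of about 0.80, while either-test dropping lifts most scenarios above it. The unrecorded choice could therefore reverse the conclusion of the kappa test. This is not a claim that 150 is too few. Because the gap sits in the statistic sized for the primary aim, it must be closed before the data are analysed.

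**What to change.** - Reconcile Aim 2, the kappa analysis and the Power and Sample Size paragraph to one analysis cut that classifies every evaluable child on both tests. One example is <5 versus ≥5, which follows Aim 2's grouping and is already a sensitivity and specificity cutoff. This concerns an analysis category, not a clinical threshold.
- Name the PSG index and the WatchPAT index that enter the table. The device reports PAHI, not OAHI.
- State that no evaluable child is left out of the kappa table because of an index value.
- Restate the kappa sizing for that index and cut, including the source of the 0.18.
- Optionally, add a weighted kappa on <2, 2 to <5, 5 to <10 and ≥10.

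The cost is wording in the aims, the analysis plan and the power paragraph, with no new data. The reported kappa may be less favourable than one computed without the middle band.

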A sample size of 147 participants achieves 80 % power at a significance level of 0.05 using a one-sided non-inferiority test of correlated proportions when the standard proportion is 0.18, the maximum allowable difference between these proportions that still results in non-inferiority (the range of non-inferiority) is 0.05 or 5%, and assuming the actual difference of the proportions is 0.0.

With 17 months enrollment and an enrollment rate of 80%, investigators anticipate enrolling 150 participants to ensure power >80% for each hypothesis test described above.

G. Summarize Knowledge to be Gained:

We hope to gain the knowledge that the WatchPAT 200 device will be able to detect OSA in children 4-12 years of age with comparable accuracy with an in-laboratory PSG.

H. References:

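### The claim is detection of OSA at any severity, but the study is sized with mild OSA counted as negative, and no planned agreement test examines the boundary between normal and mild disease

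*Combined protocol and SAP*

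**What the plan says.** Section I hypothesises that the device "will be able to detect obstructive sleep apnea in children 4 to 12 years of age as effectively as an overnight, attended, in-laboratory polysomnogram". Section G repeats the claim: "the WatchPAT 200 device will be able to detect OSA in children 4-12 years of age with comparable accuracy". Neither sets a severity limit. Aim 2 attaches the mild label to disease from 2 events/hour and describes the contrast as "detecting between normal sleep and mild (≥ 2 events per hour) versus moderate to severe obstructive sleep apnea", the last group starting at an OAHI of 5.

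The Power and Sample Size part of section IV.F says that it sizes the primary aim, which it restates: "The primary aim is to assess whether the PatWatch device agrees with PSG laboratory studies in its ability to detect OSA". It continues: "For the power analysis OSA diagnosis was dichotomized as non or mild (AHI<4.5) versus moderate or severe", the upper class being AHI of 4.5 or more. Two tests follow:

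- a kappa test with 120 participants and category frequencies 0.82 and 0.18;
- a one-sided paired non-inferiority test with 147 participants, a standard proportion of 0.18 and a 5% margin.

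The 0.18 comes from roughly 11 studies per month "with about 2 patients diagnosed with OSA". The severity of those cases is not stated.

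The Statistical Analysis Plan part of the same section plans a kappa "fixing OSA diagnosis as dichotomized as none or mild (OAHI <2 events/hour) versus moderate or severe", the second class being OAHI of 5 or more. It also plans sensitivity and specificity with 95% confidence intervals at 2, 5 and 10 events/hour.

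**The concern.** By the protocol's own labels, a child with a PSG index of 4 has mild OSA. At the 4.5 split, a device reading of 0 in that child counts as agreement. Good agreement at that split therefore says nothing about whether mild OSA is separated from normal sleep, yet the conclusion foreseen in section G is that the device detects OSA. The Background faults other alternative tests because a negative result does not exclude OSA. The boundary between normal and OSA is thus the one that the protocol's own rationale depends on.

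The frequency raises a second question. The 0.18 is described as the share diagnosed with OSA, but the kappa calculation uses it as the share with moderate or severe disease. If the 2 of 11 include mild cases, the frequency is too high for that split and the stated power does not apply to it.

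**Working it through.** **1. The cut-offs side by side.**

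| Place | Negative class | Positive class |
|---|---|---|
| Hypothesis, section G | no OSA (no cut-off given) | OSA, any severity |
| Aim 2 | normal and mild (mild from 2) | OAHI ≥5 |
| Planned kappa | OAHI <2, labelled none or mild | OAHI ≥5 |
| Power section | AHI <4.5, labelled none or mild | AHI ≥4.5 |
| Source of 0.18 | not stated | diagnosed with OSA, severity not stated |

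No row that belongs to an agreement test separates normal from mild. Under the planned kappa, a PSG value from 2 to below 5 falls in neither class. If those children are dropped, missed mild cases still cannot lower kappa.

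**2. The plan's own figures.** Enrolment: 11 × 17 × 0.80 = 149.6, or 150. Frequency: 2/11 = 0.18.

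*Kappa.* n = [(z_α·τ(κ0) + z_β·τ(κ1)) / (κ1 − κ0)]², where τ is the large-sample Fleiss–Cohen–Everitt standard deviation for two categories with equal margins. κ0 has no number in the text. With κ0 = 0.80, one-sided α = 0.05 and frequency 0.18, τ(0.80) = 0.791 and τ(0.95) = 0.408, so n = [(1.645 × 0.791 + 0.842 × 0.408) / 0.15]² ≈ 120.3. This agrees with the stated 120, but only through a back-solved κ0. A two-sided test would need κ0 = 0.767.

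*Paired 5% test.* n = (z_α + z_β)² × d / 0.05², with discordance d = 2p(1 − p)(1 − r), where r is the correlation between the two tests' results. Neither d nor r is stated. With p = 0.18 and r = 0.80, d = 0.059 and n = 146.0, or 147 when rounded up. A score version of the test would need d of about 0.040 instead.

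**3. A device that misses only mild disease.** Let moderate-to-severe disease be 0.18 of children and mild disease m (assumed, because the documents give no mild share). The device reads every mild case as normal and classifies everyone else correctly.

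At the 4.5 split the two tests never disagree, so kappa = 1.00 and the difference in proportions is 0 for any m.

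At ≥2, PSG-positive P = 0.18 + m and device-positive = 0.18. Observed agreement is 1 − m, chance agreement is p_e = 0.18P + 0.82(1 − P), kappa = (1 − m − p_e)/(1 − p_e), and sensitivity = 0.18/P.

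| m | P | p_e | Kappa at ≥2 | Sensitivity at ≥2 | Difference in proportions |
|---|---|---|---|---|---|
| 0.09 | 0.27 | 0.647 | 0.74 | 67% | 9 points |
| 0.18 | 0.36 | 0.590 | 0.56 | 50% | 18 points |
| 0.27 | 0.45 | 0.532 | 0.42 | 40% | 27 points |

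For the first row: (0.91 − 0.6472)/(1 − 0.6472) = 0.2628/0.3528 = 0.74. All three differences exceed the 5-point margin.

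**4. If 0.18 does not match the category (illustration only).**

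- *The 2 of 11 include mild cases and half are mild.* The moderate-to-severe frequency is 0.09. With κ0 = 0.80 the kappa test then needs about 220 children, and power at 150 is 55%. With κ0 = 0.767 it is 74%, and with κ0 = 0.70 it is 96%.
- *The 2 of 11 exclude mild cases and OSA at any severity is 0.36.* At r = 0.80, d = 2 × 0.36 × 0.64 × 0.20 = 0.092, and the 5% test at 147 has 64% power. At r = 0.90 it has 88%, and at r = 0.95 it has 99%. In the same scenario, kappa power at 150 rises to about 99% (κ0 = 0.80).

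**The case against.** Aim 2 can be read as grouping normal with mild, so the sizing split matches a stated aim, and sizing on a more severe threshold is a legitimate choice in what the protocol calls a pilot study. This stands for Aim 2. It does not answer the point, because the power section says that it sizes the primary aim and states that aim as detecting OSA.

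Mild disease is also not ignored. Sensitivity and specificity at 2 events/hour are planned with confidence intervals, together with Bland–Altman plots and comparisons of the indices. A device that missed mild cases would be exposed in the report. That stands too, and it limits the point: the evidence will exist, but no success criterion or sample size is attached to it.

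Three stronger readings are tempting but unsupported.

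- A reader might infer that the 5% comparison targets OSA at any severity while kappa targets moderate-to-severe disease. The 4.5 split is declared for the power analysis as a whole and both tests use 0.18, so on the plain reading both are equally blind to mild disease.
- A reader might infer that the final analysis will score missed mild cases as perfect agreement. The planned kappa uses 2 and 5, not 4.5. A child with a PSG value of 4 has no category there and is not recorded as an agreement. Kappa 1.00 belongs to the sizing split, and only if all other children are classified correctly.
- A reader might infer that the study is underpowered at 55% or 64%. Those figures need κ0 = 0.80 and r = 0.80, which the documents do not give.

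**Conclusion.** The point holds as a mismatch between the claim and the tests. The claim covers OSA of any severity, the sizing puts mild OSA in the negative class, and the planned kappa leaves PSG values of 2 to below 5 unclassified. No agreement test looks at the boundary between normal and mild. This follows from the text and depends on neither κ0 nor the discordance.

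The size of the effect depends on the mild share, which is unknown. Over the assumed 9% to 27%, with moderate-to-severe disease at 18%, a device blind to mild OSA would fall from kappa 1.00 at the 4.5 split to between 0.74 and 0.42 at ≥2, with sensitivity between 67% and 40%. The effect on power cannot be fixed from the documents: it is 55% to 96% for kappa at frequency 0.09 and N = 150 (κ0 from 0.80 to 0.70), and 64% to 99% for the 5% test at 0.36 and N = 147 (r from 0.80 to 0.95). The change should be made. It concerns definitions and the scope of the claim, and does not show that the study must fail.

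**What to change.** 1. Reconcile the definition of OSA, including AHI against OAHI, across the hypothesis, the aims, the planned kappa (2 and 5) and the power section (4.5). State where PSG and device values from 2 to below 5 are classified.
2. Then do one of two things. Either also report kappa and the paired 5% comparison for OSA present versus absent at the protocol's own mild threshold (≥2), or limit the hypothesis and section G to moderate-to-severe OSA. Which threshold is clinically right is for the investigators to settle.
3. Recount the February 2017 PSGs at each cut-off, say which severity the 2 of 11 represents, and restate power with the matching frequency and with κ0 and the discordance given as numbers.

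The cost is wording, one extra 2×2 table from data already collected, and a recount of existing studies. The downside is a narrower claim, or a less favourable stated power at one cut-off.
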